6.8.2.6.3. Antidiarrheals

For management of diarrhea related to LAM-002A, it is recommended that subjects take loperamide, 4 mg, at the occurrence of the first loose stool and then 2 mg every 2 hours until they are diarrhea-free for at least 12 hours. More aggressive loperamide prophylactic or therapeutic administration and titration of loperamide dosing for each loose bowel movement may be considered. During the night, subjects may take 4 mg of loperamide every 4 hours. Subjects should be advised to avoid dehydration through adequate fluid intake. Drugs such as 5HT3 antagonists or octreotide may be considered for their anti-secretory effects. For subjects who develop diarrhea while also receiving atezolizumab, the possibility of atezolizumab-induced colitis should be considered (see Section 6.8.4.4).

6.8.3. Rituximab or Rituximab/Hyaluronidase Human

6.8.3.1. Premedications

In accordance with rituximab/rituximab hyaluronidase human prescribing information (Genentech 2016, Genentech 2018), subjects should be premedicated with an antipyretic and an antihistamine to reduce the incidence and severity of infusion/injection reactions. A recommended regimen is diphenhydramine, 25 mg orally, and acetaminophen (paracetamol), 650 mg orally, both given ~30 minutes prior to each rituximab administration. Intravenous corticosteroids may also be administered as a premedication. Local practices and guidelines may be followed.

6.8.3.2. Rituximab Administration

Based on past experience with this regimen (Ghielmini 2004, Martinelli 2010), rituximab will be administered intravenously or rituximab/hyaluronidase human will be administered subcutaneously in the clinic for a total of 8 treatments:

Intravenous rituximab (Rituxan®)

• Four induction infusions of 375 mg/m² will be administered weekly on Cycle 1 Day 1, Cycle 1 Day 8, Cycle 1 Day 15, and Cycle 1 Day 22.

Version 9, 18 Feb 2020

• Four subsequent maintenance infusions of 375 mg/m² will be administered every 8 weeks on Cycle 4 Day 1, Cycle 6 Day 1, Cycle 8 Day 1, and Cycle 10 Day 1.

Subcutaneous rituximab (rituximab/hyaluronidase human; Rituxan Hycela®)

- An initial dose of 375 mg/mg² will be administered intravenously on Cycle 1 Day1.
- Three subcutaneous injections of 1,400 mg/23,400 Units (1,400 mg rituximab and 23,400 Units hyaluronidase human) will be administered weekly on Cycle 1 Day 8, Cycle 1 Day 15, and Cycle 1 Day 22.
- Four subsequent maintenance subcutaneous injections of 1,400 mg/23,400 Units (1,400 mg rituximab and 23,400 Units hyaluronidase human) will be administered every 8 weeks on Cycle 4 Day 1, Cycle 6 Day 1, Cycle 8 Day 1, and Cycle 10 Day 1.

The dose calculation of body surface area for infused rituximab will be based on the subject's height and actual body weight prior to therapy. Once established based on the pretreatment body weight, the total dose of rituximab for the subject should not be altered during therapy based on fluctuations in body weight unless required by institutional policy.

At Cycle 1 Day 1, ~30 minutes after administration of the required antipyretic and antihistamine premedications and ~15 to 30 minutes after administration of the first dose of LAM-002A, the first infusion of rituximab will be administered via an infusion pump. For the initial infusion, the recommended infusion rate is 50 mg/hour. In the absence of infusion toxicity, the infusion rate can be increased in 50-mg/hour increments every 30 minutes, to a maximum of 400 mg/hour.

For subsequent rituximab infusions, the required antipyretic and antihistamine premedications will be given and the rituximab will be infused via an infusion pump. For these infusions, the infusion can be initiated at 100 mg/hour. In the absence of infusion toxicity, the infusion rate can be increased in 100-mg/hour increments every 30 minutes, to a maximum of 400 mg/hour. Alternatively, for subjects who tolerate the first infusion with Grade \leq 3 infusion toxicity, subsequent infusions can be administered over a planned infusion time of 90 minutes, with \sim 20% of the total dose administered in the first 30 minutes and the remaining 80% of the total protein dose administered in the subsequent 60 minutes (Dakhil 2014, Genentech 2016).

For subsequent rituximab/hyaluronidase human injections, the required antipyretic and antihistamine premedications will be given and the rituximab/hyaluronidase human will be injected into the subcutaneous tissue of the abdomen over ~5 minutes. Areas where the skin is red, bruised, tender or hard, or areas where there are moles or scars should be avoided. No data are available on performing the injection at other sites of the body. If administration of rituximab/hyaluronidase human is interrupted, drug administration can continue at the same site or at a different site but restricted to the abdomen. Patients should be observed for ≥15 minutes following the completion of injection. During treatment with rituximab/hyaluronidase human, do not administer other medications for subcutaneous use at the same sites.

Version 9, 18 Feb 2020

6.8.3.3. Management of Rituximab Infusion/Injection Toxicity

Rituximab can cause severe, including fatal, infusion reactions (Genentech 2016). Patients with pre-existing cardiac or pulmonary conditions, those who experienced prior cardiopulmonary adverse reactions to rituximab, and those with high numbers of circulating malignant cells (≥25 x 10⁹/L) may be at particular risk. Severe reactions typically occur during the first infusion and are generally less frequent and less severe with subsequent infusions. The time to onset of infusion toxicity ranges from 30 to 120 minutes. Rituximab-induced infusion reactions and sequelae include urticaria, hypotension, angioedema, hypoxia, bronchospasm, pulmonary infiltrates, acute respiratory distress syndrome, myocardial infarction, ventricular fibrillation, cardiogenic shock, and/or anaphylactoid events.

Rituximab infusions/injections should be interrupted or slowed in subjects experiencing Grade ≥3 rituximab-related infusion reactions. Medical management (eg, oxygen, epinephrine, bronchodilators, and/or glucocorticoids) should be instituted, as needed. Upon improvement of symptoms, the infusion may be continued at 50% of the previous rate. At the discretion of the investigator, rituximab therapy may be permanently discontinued in subjects with Grade 4 infusion/injection reactions or with reactions requiring substantial intervention.

6.8.3.4. Rituximab/Rituximab Hyaluronidase Human Dose Modifications and Supportive Care

Rituximab-related noninfectious pneumonitis has been described (Subramanian 2010) with an incidence of ~4.3% (Salmasi 2010). In patients developing rituximab-associated pneumonitis, the mean time from the first rituximab infusion to the onset of respiratory symptoms was 3 months, with a peak incidence after administration of a mean cumulative dosage of 1600 mg/m2 (Lioté 2010).

Severe, including fatal, mucocutaneous reactions can occur in patients receiving rituximab during infusion or at later timepoints. Non-infusion related events have included paraneoplastic pemphigus, Stevens Johnson syndrome, lichenoid dermatitis, vesiculobullous dermatitis, and toxic epidermal necrolysis (Genentech 2016). The onset of these reactions has varied from 1 to 13 weeks following initiation of rituximab exposure.

Among patients receiving rituximab in combination with chemotherapy, rare instances of life-threatening bowel obstruction or perforation has been observed (Ram 2009), primarily in patients with NHL. In post-marketing reports, the mean time to documented gastrointestinal perforation was 6 (range 1–77) days from start of chemoimmunotherapy.

Fulminate and fatal HBV infection and reactivation can occur during or after treatment with rituximab (Genentech 2016). The risk is very low among patients with negative anti-HBc serology (Matsue 2010) and/or undetectable HBV DNA as assessed by quantitative PCR. Because subjects with such evidence of persistent HBV infection are excluded from this study, reactivation is not anticipated. Other serious bacterial, fungal, and new or reactivated viral infections have also occurred during and for ~1 year following rituximab-based therapy (Gea-Banacloche 2010). Other new or reactivated viral infections in patients receiving rituximab have included CMV, herpes simplex virus, parvovirus B19, varicella zoster virus, West Nile

Version 9, 18 Feb 2020

virus, and HCV. Progressive multifocal leukoencephalopathy (PML) due to polyomavirus JC has been observed in patients who have received rituximab therapy for hematologic malignancies (Carson 2009).

No dose reductions of rituximab/rituximab hyaluronidase human are recommended. If a subject experiences an AE that is suspected to be related to rituximab/rituximab hyaluronidase human and is of sufficient severity to warrant modification of therapy, administration of the drug should be interrupted or discontinued. Protocol-recommended management of selected adverse events and appropriate supportive care is described in Table 5.

Table 5: Recommended Rituximab or Rituximab/Hyaluronidase Modifications and Supportive Care

Adverse Event	Rituximab Interruption and Resumption	Rituximab Permanent Discontinuation	Supportive Care
Pneumonitis	Interrupt for Grade 2; resume when Grade ≤ 1	Grade ≥3	For Grade ≥2, corticosteroids, 1-2 mg/kg of prednisone equivalents
Rash	Interrupt for Grade 3; resume when Grade ≤ 1	Grade 4	For Grade 2, topical corticosteroids. For Grade ≥ 3, corticosteroids, 1-2 mg/kg of prednisone equivalents
Hepatitis	Grade ≥3 elevations of serum AST or ALT (> 5 x ULN); resume when Grade ≤ 1		Evaluate for HBV positivity; if HBV reactivation, treat with appropriate antiviral considering any potential for drug-drug interaction with LAM-002A.
Bowel obstruction or perforation		Any grade	Provide appropriate antibiotic therapy and surgical supportive care.
Infection	Grade ≥3; resume when control of infection achieved		Treat with appropriate systemic antibiotics for suspected or confirmed infections

Abbreviations: ALT=alanine aminotransferase, AST=aspirate aminotransferase, ULN=upper limits of normal

Version 9, 18 Feb 2020

6.8.4. Atezolizumab

6.8.4.1. Premedications

No specific premedications are recommended for administration prior to atezolizumab administration. Given the potential for interference with desired atezolizumab immunopotentiation, systemic corticosteroid administration should be avoided.

6.8.4.2. Atezolizumab Administration

Atezolizumab will be administered intravenously in the clinic every 3 weeks. The dose for each infusion will be 1200 mg.

Using an infusion pump, atezolizumab should be administered through an intravenous line with or without a sterile, non-pyrogenic, low-protein binding in-line filter (pore size of 0.2 to 0.22 μ m). Other drugs should not be coadministered with atezolizumab through the same intravenous line.

At Cycle 1 Day 1, ~15 to 30 minutes after administration of the first dose of LAM-002A, the first infusion of atezolizumab will be administered over 60 minutes. If the first infusion is tolerated, all subsequent infusions may be delivered over 30 minutes. Atezolizumab should not be administered as an intravenous push or bolus.

6.8.4.3. Management of Atezolizumab Infusion Toxicity

While infrequent (incident <2%), severe infusion reactions have occurred in clinical trial subjects receiving atezolizumab. For subjects with Grade 1 or 2 infusion reactions, the atezolizumab infusion should be interrupted or slowed. For subjects with Grade \geq 3 infusion reactions, atezolizumab therapy should be permanently discontinued.

6.8.4.4. Atezolizumab Dose Modifications and Supportive Care

In clinical trials supporting its approval as therapy for patients with previously treated advanced non-small cell lung cancer and metastatic bladder cancer (Weinstock 2017, Ning 2017), atezolizumab administration has been associated with immune-related AEs of pneumonitis, hepatitis, pancreatitis, colitis, endocrinopathies (hypophysitis, thyroiditis, adrenal insufficiency, diabetes mellitus), and neurological toxicity (meningitis/encephalitis, motor/sensory neuropathies, myasthenic syndrome/myasthenia gravis, Guillain-Barré syndrome). Immune-related AEs can be observed within days to months after starting atezolizumab therapy (Genentech 2017).

Severe infections, including pneumonias, urinary tract infections, sepsis, herpes encephalitis, and mycobacterial infection have occurred.

Systemic immune activation is a rare condition characterized by an excessive immune response. Given the mechanism of action of atezolizumab, systemic immune activation is considered a potential risk when atezolizumab is given in combination with other immunomodulating agents. Systemic immune activation should be included in the differential diagnosis for study subjects who, in the absence of an alternative etiology, develop a sepsis-like syndrome after administration of atezolizumab. The initial evaluation should include:

• CBC with peripheral smear

Version 9, 18 Feb 2020

- PT, PTT, fibrinogen, and D-dimer
- Ferritin
- Triglycerides
- AST, ALT, and total bilirubin
- LDH
- Complete neurologic and abdominal examination (assessing for hepatosplenomegaly)

If systemic immune activation is suspected after the initial evaluation, the medical monitor should be contacted in consultation.

Reference should be made to Section 6 of the atezolizumab investigator brochure for a detailed description of anticipated safety risks for atezolizumab.

No dose reductions of atezolizumab are recommended. If a subject experiences an AE that is suspected to be related to atezolizumab and is of sufficient severity to warrant modification of therapy, administration of the drug should be interrupted or discontinued. Protocol-recommended management of selected adverse events is described in Table 6.

 Table 6:
 Recommended Atezolizumab Modifications and Supportive Care

Adverse Event	Atezolizumab Interruption and Resumption	Atezolizumab Permanent Discontinuation	Supportive Care
Pneumonitis	Interrupt for Grade 2; resume when Grade ≤ 1	Grade ≥3	For Grade ≥2, corticosteroids, 1-2 mg/kg of prednisone equivalents
Hepatitis	Interrupt for Grade 2 elevations of serum AST or ALT (> 3-5 x ULN) or total bilirubin (> 1.5-3 x ULN); resume when Grade ≤ 1	Grade ≥3 elevations of serum AST or ALT (> 5 x ULN) or total bilirubin (> 3 x ULN)	For Grade ≥2, corticosteroids, 1-2 mg/kg of prednisone equivalents
Colitis	Interrupt for Grade 2 or 3; resume if Grade ≤ 1 within 12 weeks on ≤ 10 mg oral prednisone equivalents	Grade 4	For Grade 2 recurrent or persistent (> 5 days), corticosteroids, 1-2 mg/kg of prednisone equivalents; For Grade ≥3, methylprednisolone 1-2 mg/kg intravenous → oral corticosteroid taper over ≥ 1 month

Version 9, 18 Feb 2020

Adverse Event	Atezolizumab Interruption and Resumption	Atezolizumab Permanent Discontinuation	Supportive Care
Pancreatitis	Interrupt for Grade 2 or 3 pancreatitis or Grade ≥3 increases in serum amylase or lipase levels (>2 x ULN); resume if Grade ≤ 1 within 12 weeks on ≤ 10 mg oral prednisone equivalents	Grade 4 pancreatitis or any grade of recurrent pancreatitis	For Grade ≥2, methylprednisolone 1-2 mg/kg intravenous → oral corticosteroid taper over ≥ 1 month
Hypophysitis	Interrupt for symptoms; resume when Grade ≤ 1		Administer corticosteroids and hormone replacement as clinically indicated
Thyroid disorders	Interrupt for symptoms; resume when Grade ≤ 1		For symptomatic hypo- or hyperthyroidism, initiate hormone replacement or anti-thyroid drug, as needed
Adrenal insufficiency	Interrupt for symptoms; resume if Grade ≤ 1 within 12 weeks on ≤ 10 mg oral prednisone equivalents		For symptoms, methylprednisolone 1-2 mg/kg intravenous → oral corticosteroid taper over ≥ 1 month
Diabetes mellitus	Interrupt for Grade ≥3 hyperglycemia (serum glucose ≥ 250 mg/dL; resume when blood sugar control achieved	-	Insulin for Type 1 diabetes mellitus
Meningitis, encephalitis, myasthenic syndrome, myasthenia gravis, or Guillain- Barré syndrome		Any grade	Methylprednisolone 1-2 mg/kg intravenous → oral corticosteroid taper over ≥ 1 month
Rash	Interrupt for Grade 3; resume when Grade ≤ 1	Grade 4	For Grade 2, topical corticosteroids. For Grade ≥ 3, corticosteroids, 1-2 mg/kg of prednisone equivalents

Version 9, 18 Feb 2020

Adverse Event	Atezolizumab Interruption and Resumption	Atezolizumab Permanent Discontinuation	Supportive Care
Infection	Grade 3 or 4; resume when control of infection achieved		Treat with appropriate systemic antibiotics for suspected or confirmed infections

Abbreviations: ALT=alanine aminotransferase, AST=aspirate aminotransferase, ULN=upper limits of normal

6.9. Other Supportive Care Recommendations

Consistent with subject safety and comfort, administration of any prescription or over-the-counter drug products other than study medication will be minimized during the study period. Subjects should be discouraged from use of herbal remedies, self-prescribed drugs, tobacco products, or street drugs during their participation in the clinical study and should be counseled to minimize use of alcohol or nonmedical marijuana.

If considered necessary for the subject's well-being, drugs for concomitant medical conditions or for symptom management may be given at the discretion of the investigator. The investigator's decision to authorize the use of any drug other than study drug will take into account subject safety, the medical need, the potential for drug interactions, the possibility for masking symptoms of a more significant underlying event, and whether use of the drug will compromise the outcome or integrity of the study.

Subjects will be instructed about the importance of the need to inform the clinic staff of the use of any drugs or remedies (whether prescribed, over-the-counter, or illicit) before and during the study.

Recommendations regarding specific types of concomitant therapies, supportive care, diet, and other interventions are provided below. To minimize variations in supportive care, the recommended supportive care agents (eg, loperamide, granisetron) should be used unless there is a medical rationale in a specific subject for use of an alternative product.

6.9.1. Antibiotics, Antifungals, and Antivirals

Care should be taken to avoid or minimize concomitant administration of prophylactic or therapeutic antibacterial, antifungal, or antiviral, agents that are moderate or strong CYP3A4 or CY2C9 inhibitors or inducers (see Section 6.9.6 and Appendix 3).

For subjects with a history of recurrent infections, prophylaxis with intravenous gamma-globulin may be offered and consideration may be given to initiation of antibiotic prophylaxis against pneumocystis infection (eg, with trimethoprim-sulfamethoxazole, dapsone, aerosolized pentamidine, or atovaquone) beginning prior to study drug administration. Such support also offers the benefit of reducing the risk for other bacterial infections (Stern 2014). Local practices or guidelines regarding infection prophylaxis may be followed.

Subjects developing an intercurrent infection during study drug treatment may receive therapeutic antibacterial, antiviral, or antifungal drugs for intercurrent infections as needed. Continuation of study therapy during treatment for an intercurrent infection is at the discretion of

the investigator but guidance in Section 6.8.3.4 and Section 6.8.4.4 should be considered in subjects receiving combination therapy.

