6.9.6. Drugs with Potential for Drug-Drug Interactions with LAM-002A

No information is available regarding interactions of LAM-002A with therapeutic agents or other substances in humans. *In vitro* data suggest that concomitant administration of potent inhibitors or inducers of CYP3A4 or CYP2C9 might alter LAM-002A clearance and lead to clinically

significant increases or decreases in LAM-002A exposure. Consequently, the concomitant use of strong inhibitors or inducers of CYP3A4 or CYP2C9 (see Table 15) should be avoided when possible.

Based on these considerations, protocol candidates who require therapy with strong CYP3A4 or CYP2C9 inhibitors or inducers listed in Table 15 should not be enrolled into the study.

During study participation, coadministration of LAM-002A with CYP3A4 or CYP2C9 inhibitors or inducers (see Table 15) should be avoided, if possible. However, a subject who develops a condition that may require use of such drugs is not required to permanently discontinue LAM-002A if the subject is experiencing clinical benefit and other options for treating the subject's cancer are limited. If medically appropriate, investigators may wish to use a therapeutic alternative that would not be expected to affect these enzymes. For subjects who require temporary use of a drug that does affect these enzymes (e.g., treatment with a systemic antifungal agent), LAM-002A can be interrupted (or the doses reduced) during use of the other medication and then resumed after completion of the other drug. For subjects who require initiation of chronic therapy with a drug that potently affects these enzymes, investigators must consult with the medical monitor to consider the best course of action.

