6.9.7. Drugs Known to Prolong the OT Interval

In a thorough QTc study, apilimod dimesylate at doses of 50 mg and 150 mg was associated with repolarization findings in excess of those deemed negative by regulatory guidance. The magnitude of the change was modest (~8.5 msec), peaked at 4 hours and did not demonstrate a dose trend. Preliminary QTc observations in the ongoing study in patients with hematological malignancies suggest the potential for dose- and exposure dependent Grade 1 or 2 QT prolongation.

As a precaution, the clinical potential of LAM-002A to prolong the QT interval will be assessed in this study. Accordingly, co-administration of LAM-002A and known QT-prolonging drugs is to be minimized because use of such drugs might confound interpretation of QT data from the trial.

Based on these considerations, protocol candidates who require therapy with drugs known to prolong the QT interval (as listed in Table 16) should not be enrolled into the study. If medically justified, protocol candidates may be enrolled if such drugs can be discontinued or alternative drugs that do not affect QT can be substituted >7 days before the first dose of study drug.

After the subject is enrolled to the protocol, use of drugs known to prolong the QT interval should be minimized but is not prohibited if administration of such drug is necessary and the subject appears to be benefiting from protocol therapy.

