- 17. Stage 2 (study candidates being considered for LAM-002A/atezolizumab combination therapy): Active or history of autoimmune disease or immune deficiency, including, but not limited to, myasthenia gravis, myositis, autoimmune hepatitis, systemic lupus erythematosus, rheumatoid arthritis, inflammatory bowel disease, antiphospholipid

Version 9, 18 Feb 2020

antibody syndrome, Wegener granulomatosis, Sjögren syndrome, Guillain-Barré syndrome, or multiple sclerosis (with the following exceptions: history of autoimmune-related hypothyroidism and receiving thyroid-replacement hormone; controlled Type 1 diabetes mellitus on an insulin regimen; eczema, psoriasis, lichen simplex chronicus, or vitiligo with dermatologic manifestations if rash covers < 10% of body surface area, disease is well controlled at baseline and requires only low-potency topical corticosteroids, there is no occurrence of acute exacerbations of the underlying condition requiring psoralen plus ultraviolet A radiation, methotrexate, retinoids, biologic agents, oral calcineurin inhibitors, or high-potency or oral corticosteroids within the previous 12 months, and the subject does not have extra-cutaneous disease [e.g., psoriatic arthritis]).

- 18. The subject has a history of malabsorption or other GI disease that may significantly alter the absorption of apilimod (e.g., \geq Grade 2 nausea, vomiting or diarrhea).
- 19. The subject has undergone major surgery within 28 days prior to first dose of study drug.
- 20. The subject has a QTcF > 470 msec on screening ECG or has a history or risk factors for, or use of medications known to prolong QTc interval or that may be associated with Torsades de Pointes within 7 days of treatment start.
- 21. The subject has past history of tuberculosis (TB) or active infection with TB, human immunodeficiency virus (HIV), hepatitis B virus (HBV) or hepatitis C virus (HCV). Note: Subjects must have negative human immunodeficiency virus (HIV) antibody, negative hepatitis B surface antigen (HBsAg) and negative hepatitis B core (HBc) antibody or undetectable HBV deoxyribonucleic acid (DNA) by quantitative polymerase chain reaction (PCR) testing, and negative HCV antibody or negative HCV ribonucleic acid (RNA) by quantitative PCR.
- 22. The subject is lactating and breast feeding.
- 23. The subject has a previously identified allergy or hypersensitivity to components of the study treatment formulation.

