Appendix 3. Potential Drug Interactions with LAM-002A

Table 15: CYP2C9 and CYP3A Inhibitors and Inducers

	CYP2C9 In	hibitors Z	
Strong	Moderate	Weak	Other
fluconazole Strong	CYP2C9 Moderate	Inducers Weak	efavirenz isoniazid metronidazole paroxetine sulfamethoxazole voriconazole Other carbamazepine nevirapine
			phenobarbital rifampin St. John's Wort
	CYP3A In	hhibitors Weak	Other
Boceprevir Clarithromycin Cobicistat Conivaptan Fluvoxamine Grapefruit Juice (in large amounts, > 1 liter a day, and in high concentrations) Indinavir Itraconazole Ketoconazole Lopinavir and Ritonavir Nefazodone Nelfinavir Posaconazole Quinupristin Ritonavir	Aprepitant Atazanavir Ciprofloxacin Darunavir Diltiazem Dronedarone Erythromycin Fluconazole Fosamprenavir Grapefruit Juice (in lower concentrations and smaller amounts) Imatinib Verapamil	Alprazolam Amiodarone Amlodipine Atorvastatin Bicalutamide Cilostazol Cimetidine Cyclosporine Fluoxetine Ginkgo Goldenseal Imipramine Isoniazid Nilotinib Oral contraceptives Ranitidine Ranolazine	Azithromycin Bromocriptine Chloramphenicol Delavirdine Desipramine Danazol Felodipine Iloperidone Linagliptin Nicardipine Nifedipine Quinidine Simeprevir Zafirlukast

Version 9, 18 Feb 2020

Table 15: CYP2C9 and CYP3A Inhibitors and Inducers (Continued)

CYP3A Inhibitors			
Strong	Moderate	Weak	Other
Saquinavir		Tipranavir	
Telaprevir		Zileuton	
Telithromycin			
Voriconazole			
	CYP3	A Inducers	·
Strong	Moderate	Weak	Other
Carbamazepine	Bosentan	Aprepitant	Dexamethasone
Phenobarbital	Efavirenz	Armodafinil	Felbamate
Phenytoin	Etravirine	Echinacea	Fosamprenavir
Rifampin	Modafinil	Pioglitazone	Griseofulvin
St. John's Wort	Nafcillin	Prednisone	Nevirapine
		Rufinamide	Oxcarbazepine
		Topiramate	Rifabutin
			Rifapentine
			Tocilizumab
			Tumor Necrosis Factor inhibitors

Source: Flockhart 2007

Clinical Study Report 16.1 Study Information

Protocol: LAM-002A-NHL-CLN01

Table 16: Drugs Known to Prolong the QT Interval and/or Cause Torsades De Pointes (TDP)

(IDP)		T	
Generic Name	Brand Names (Partial List)	Drug Class	Therapeutic Use
Amiodarone	Cordarone®, Pacerone®, Nexterone®	Antiarrhythmic	Abnormal heart rhythm
Anagrelide	Agrylin®, Xagrid®	Phosphodiesterase 3 inhibitor	Thrombocythemia
Arsenic trioxide	Trisenox®	Anticancer	Cancer (leukemia)
Astemizole (removed from market)	Hismanal®	Antihistamine	Allergic rhinitis
Azithromycin	Zithromax®, Zmax®	Antibiotic	Bacterial infection

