Haloperidol	Haldol® (US & UK), Aloperidin®, Bioperidolo®, Brotopon®, Dozic®, Duraperidol® (Germany), Einalon S®, Eukystol®, Halosten®, Keselan®, Linton®, Peluces®, Serenace®, Serenase®, Sigaperidol®	Antipsychotic	Schizophrenia, agitation
Ibogaine (only on non-US market)	None	Psychedelic	Narcotic addiction, unproven
Ibutilide	Corvert®	Antiarrhythmic	Abnormal heart rhythm
Levofloxacin	Levaquin®, Tavanic®	Antibiotic	Bacterial infection
Levomepromazine (methotrimeprazine) only on non-US market)	Nosinan®, Nozinan®, Levoprome®	Antipsychotic	Schizophrenia
Levosulpiride (only on non-US market)	Lesuride®, Levazeo®. Enliva® (with rabeprazole)	Antipsychotic	Schizophrenia
Levomethadyl acetate (removed from market)	Orlaam®	Opioid agonist	Narcotic dependence
Mesoridazine (removed from market)	Serentil®	Antipsychotic	Schizophrenia
Methadone	Dolophine®, Symoron®, Amidone®, Methadose®,	Opioid agonist	Narcotic dependence, pain

Generic Name	Brand Names (Partial List)	Drug Class	Therapeutic Use
	Physeptone®, Heptadon®		
Moxifloxacin	Avelox®, Avalox®, Avelon®	Antibiotic	Bacterial infection
Ondansetron	Zofran®, Anset®, Ondemet®, Zuplenz®, Emetron®, Ondavell®, Emeset®, Ondisolv®, Setronax®	Antiemetic	Nausea, vomiting
Oxaliplatin	Eloxatin®	Antineoplastic Agent	Cancer
Papaverine HCl	none	Vasodilator, Coronary	Diagnostic adjunct
Pentamidine	Pentam®	Antifungal	Fungal infection (Pneumocystis pneumonia)
Pimozide	Orap®	Antipsychotic	Tourette's Disorder
Probucol (removed from market)	Lorelco®	Antilipemic	Hypercholesterolemia
Procainamide	Pronestyl®, Procan®	Antiarrhythmic	Abnormal heart rhythm
Propofol	Diprivan®, Propoven®	Anesthetic, general	Anesthesia
Quinidine	Quinaglute®, Duraquin®, Quinact®, Quinidex®, Cin-Quin®, Quinora®	Antiarrhythmic	Abnormal heart rhythm
Roxithromycin (only on non-US market)	Rulide®, Xthrocin®, Roxl-150®, Roxo®, Surlid®, Rulide®, Biaxsig®, Roxar®, Roximycinv®, Roxomycin®, Rulid®, Tirabicin®, Coroxin®	Antibiotic	Bacterial infection
Sevoflurane	Ulane®, Sojourn®	Anesthetic, general	Anesthesia
Sotalol	Betapace®, Sotalex®, Sotacor®	Antiarrhythmic	Abnormal heart rhythm
Sparfloxacin (removed from market)	Zagam®	Antibiotic	Bacterial infection
Sulpiride (only on non-US market)	Dogmatil®, Dolmatil®, Eglonyl®, Espiride®, Modal®, Sulpor®	Antipsychotic, atypical	Schizophrenia
Sultopride (only on non-US market)	Barnetil®, Barnotil®, Topral®	Antipsychotic, atypical	Schizophrenia
Terfenadine (removed from market)	Seldane®	Antihistamine	Allergic rhinitis

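### Section 6.9.1 names aerosolized pentamidine as prophylaxis to start before study drug, but Table 16, exclusion 20 and Section 6.9.7 make its use within 7 days of treatment start an eligibility failure as written

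*Combined protocol and SAP*

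**What the plan says.** Section 6.9.1 makes the prophylaxis optional: for subjects with a history of recurrent infections, investigators may consider starting "antibiotic prophylaxis against pneumocystis infection (eg, with trimethoprim-sulfamethoxazole, dapsone, aerosolized pentamidine, or atovaquone) beginning prior to study drug administration". That sentence gives both the four examples and the timing. The only drug-interaction caution in that section concerns moderate or strong CYP3A4 or CYP2C9 inhibitors and inducers. It refers the reader to Section 6.9.6 and Appendix 3, gives no QT caution and does not cite Section 6.9.7.

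The QT provisions are elsewhere:

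- Appendix 3, Table 16 lists pentamidine, gives pneumocystis pneumonia as its use, and states no limit by route.
- Exclusion 20 (Section 7.2, repeated in the Synopsis) excludes "use of medications known to prolong QTc interval or that may be associated with Torsades de Pointes within 7 days of treatment start".
- Section 6.9.7 says "protocol candidates who require therapy with drugs known to prolong the QT interval (as listed in Table 16) should not be enrolled". It allows entry if the drug is stopped or replaced more than 7 days before the first dose. After enrolment, listed drugs are to be kept to a minimum but are not forbidden.

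On CYP interactions, the third paragraph of Section 6.9.6 says "coadministration of LAM-002A with CYP3A4 or CYP2C9 inhibitors or inducers (see Table 15) should be avoided, if possible". The first paragraph of the same section limits the precaution to strong agents.

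**The concern.** A site reading the anti-infective section alone would see pentamidine offered as an acceptable agent to have running before the first dose. A site reading the exclusion criteria would turn the same candidate away. Both would be following the protocol.

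Two things are at stake. The first is eligibility, since the result is either a deviation at entry or different handling of similar candidates across sites. The second is the QT assessment. Sections 4.1.4.3 and 6.9.7 report a change of about 8.5 msec in a thorough QT study and a possible dose- and exposure-dependent Grade 1 or 2 prolongation in this trial. Section 6.9.7 says QT will be assessed here, and that listed drugs are to be minimized because they might confound its interpretation. The serial ECGs fall on Cycle 1 Days 1 and 8 (Days 1 and 10 on the intermittent schedule), when prophylaxis begun beforehand would be in use.

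**Working it through.** The plan states no figure on this point, so the check is a cross-reference of each agent named in Section 6.9.1 against the lists and rules.

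| Agent in 6.9.1 | Table 16 (QT) | Table 15 (CYP) | Exclusion 20 (QT drugs, 7 days) | Exclusion 12 (strong CYP agents) | 6.9.6, third paragraph |
|---|---|---|---|---|---|
| Aerosolized pentamidine | Listed, no route stated | Not listed | Met if used in the window | Not met | Not covered |
| Trimethoprim-sulfamethoxazole | Not listed | "sulfamethoxazole" listed as a CYP2C9 inhibitor, apparently in the Other column | Not met | Not met | Covered: avoid if possible |
| Dapsone | Not listed | Not listed | Not met | Not met | Not covered |
| Atovaquone | Not listed | Not listed | Not met | Not met | Not covered |

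**Pentamidine, step by step.**

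1. Section 6.9.1 has the agent begin before study drug.
2. Prophylaxis that starts before dosing and continues into it is in use within the last 7 days, unless the last administration fell earlier. The protocol does not say how use is counted for an agent given at intervals.
3. Table 16 makes no distinction by route, so the aerosolized form is covered as written.
4. Exclusion 20 turns on use of the drug, not on need for it, so it is met.
5. Section 6.9.7 turns on need. It conflicts as well if pentamidine is the agent the candidate requires.
6. The softer on-study rule in Section 6.9.7 does not help, because the conflict arises at entry.

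The count is therefore one agent of four in conflict with an eligibility rule, one in tension with a qualified precaution only, and two with no conflict.

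**CYP scope.** The on-study precaution appears three times:

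| Place | Agents covered | Strength of the rule |
|---|---|---|
| 6.9.1, first paragraph | Moderate or strong | Avoid or minimize |
| 6.9.6, first paragraph | Strong | Avoid when possible |
| 6.9.6, third paragraph | Any Table 15 inhibitor or inducer | Avoid if possible |

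The third scope reaches drugs that the protocol itself offers or requires. These are sulfamethoxazole (Section 6.9.1), oral contraceptives (recommended in Table 7, weak CYP3A inhibitors in Table 15) and dexamethasone (required with intermittent dosing in Section 6.8.2.6.2, a CYP3A inducer in Table 15). The first two scopes reach none of them, if sulfamethoxazole is in the Other column. The layout of Table 15 is broken in the text available, so that column is inferred.

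**The case against.** The other side has a fair case. The prophylaxis is optional, the agents are examples, and two of the four are on neither list. With those in the same sentence, pentamidine need not be required, so Section 6.9.7 may not apply. Under Section 6.4 the investigator and then the contract research organization review eligibility before dosing, and Section 6.9 asks investigators to weigh interactions and study integrity for any co-medication. The CYP precautions are all qualified.

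Much of this stands, and it limits the point to one agent in one window. It does not remove the conflict. Exclusion 20 needs only use, and an eligibility review that works would reject a candidate managed according to a named example.

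A reader might infer more than the documents support:

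- *That trimethoprim-sulfamethoxazole also breaches an exclusion.* Exclusion 20 concerns QT and torsades drugs, and neither component is in Table 16. Exclusion 12 covers strong CYP agents, and sulfamethoxazole is not shown as one.
- *That the PK data would be distorted.* Section 6.9.6 is concerned with potent agents. Although it names CYP2C9, the phenotyping in Section 4.1.2 names CYP3A4 and, to a lesser extent, CYP1A2 and CYP2D6. No effect of sulfamethoxazole on exposure is shown.
- *That the QT bias can be sized by dividing an assumed effect by a cohort of 3 to 6.* The documents give no QT effect for aerosolized pentamidine. Prophylaxis started before dosing would also be present at the Cycle 1 Day 1 predose ECG, so a change from that value would largely remove it.
- *That the analysis plan lacks a flag for such records.* Section 14.2 defers detail to the SAP, and only part 1 of 2 of the document is available.

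**Conclusion.** The contradiction over pentamidine is real and rests on the text alone. A subject given this agent within 7 days of treatment start follows Section 6.9.1 and is ineligible under exclusion 20. This assumes that Table 16 is the reference list for exclusion 20, which does not cite it, and that the absence of a route limit means all routes are covered. If the sponsor intends the aerosolized route to be exempt, nothing in the documents says so.

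The size is one named agent of four, among subjects with recurrent infections. The documents do not say how many such subjects are expected. The effect on QT data is the one Section 6.9.7 states, possible confounding, and no more.

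The three CYP scopes are a lesser inconsistency of wording. They matter because the broadest one conflicts with drugs the protocol recommends or requires. The pentamidine conflict should be corrected because it bears on eligibility and safety and is cheap to resolve.

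**What to change.** Reconcile Section 6.9.1 with Table 16, exclusion 20 and Section 6.9.7, and state whether the aerosolized route falls under Table 16 and exclusion 20. Which way to resolve it is a clinical decision for the sponsor. Adding a reference to Section 6.9.7 in Section 6.9.1 would bring the QT rule to the reader's notice.

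Use one CYP scope in Sections 6.9.1 and 6.9.6, and check it against Table 7 and Section 6.8.2.6.2, so that no drug is both recommended or required and to be avoided.

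The cost is a few sentences in an amendment, with no change to design, sample size or visits. As an option, ECG records taken while a Table 16 drug is in use could be flagged from the concomitant-medication data, which are already collected and coded.
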